4.4. End of Study Definition

A participant is considered to have completed the study if he/she has completed all required phases of the study including the last scheduled procedure shown in the SoA (Section 1.3).

The end of the study is defined as the date of last scheduled procedure shown in the SoA for the last participant in the trial globally.

5. Study Population

Prospective approval of protocol deviations to recruitment and enrollment criteria, also known as protocol waivers or exemptions, is not permitted.

5.1. Inclusion Criteria

Participants are eligible to be included in the study only if all of the following criteria apply:

Age

1. Are ≥ 18 years of age, at the time of signing the informed consent

Type of Participant and Disease Characteristics

2. Have a diagnosis of adult onset RA as defined by the 2010 American College of Rheumatology (ACR)/European League Against Rheumatism (EULAR) classification criteria (Aletaha et al. 2010) for at least 3 months prior to screening
3. Have moderately to severely active RA defined by the presence of ≥ 6 swollen joints (based on 66 joint count) and ≥ 6 tender joints (based on 68 joint count) at screening and baseline. The distal interphalangeal joint should be evaluated but not included in the total count to determine eligibility
4. Have at least 1 of the following:
 - positive test results for rheumatoid factor or anti-citrullinated peptide antibodies at screening,
OR
 - previous radiographs documenting bony erosions in hands or feet consistent with RA
5. Have C-reactive protein (CRP) >1.2 times upper limit of normal (ULN) per the central laboratory at screening
6. Have active synovitis in ≥ 1 joint in hands or wrists at screening as demonstrated by a MRI synovitis RAMRIS score ($\ddot{\text{O}}\text{stergaard}$ et al. 2017) of ≥ 1 determined from central reading of images
7. Vaccinations of study subjects should be up to date per regional and national guidelines, specifically influenza, pneumonia, and zoster. All should be administered ≥ 30 days before randomization and no live vaccines should be used within 3 months of randomization
8. Have clinically acceptable central laboratory test results at screening (retesting is allowed for hematology and chemistry), as assessed by the investigator, including:
 - Hematology
 - absolute neutrophil count $\geq 1.5 \times 10^9/\text{L}$ ($\geq 1.5 \times 10^3/\mu\text{L}$ or $\geq 1.5 \text{ GI/L}$)
 - platelet count $\geq 100 \times 10^9/\text{L}$ ($\geq 100 \times 10^3/\mu\text{L}$ or $\geq 100 \text{ GI/L}$)
 - hemoglobin level $\geq 10.0 \text{ g/dL}$

- lymphocyte count >500 cells/ μ L ($>0.50 \times 10^3/\mu$ L or >0.50 GI/L)
- total leukocyte count $\geq 3.0 \times 10^9/L$ ($\geq 3.0 \times 10^3/\mu$ L or ≥ 3.0 GI/L)

Clinical chemistry test results

- serum creatinine, alanine aminotransferase (ALT), and aspartate aminotransferase (AST) levels $\leq 2 \times$ ULN
- total bilirubin level (TBL) and alkaline phosphatase (ALP) $< 1.5 \times$ ULN (patients with Gilbert's syndrome must have serum direct bilirubin < 1.5 mg/dL)

Concomitant Therapy

9. Demonstrated an inadequate response to, or loss of response or intolerance to:

- at least 1 csDMARD treatment
- OR
- at least 1 bDMARD/tsDMARD treatment

This is defined as signs and symptoms of persistently active disease despite a history of treatment with at least 1 of the following: azathioprine, MTX, hydroxychloroquine, leflunomide, sulfasalazine, bDMARDs, or tsDMARDs

10. The following therapies are permitted during the study, if the dose is stable for ≥ 4 weeks prior to the screening MRI:

- parenteral MTX up to 20 mg/week OR oral MTX up to 25 mg/week. Subjects on MTX should receive supplementation with folic acid according to local standard of care
- hydroxychloroquine up to 400 mg/day
- leflunomide up to 20 mg/day
- oral sulfasalazine up to 3000 mg/day
- oral prednisone ≤ 10 mg daily or other equivalent corticosteroid dose

Contraception

11. To participate in the study, participants must agree to the reproductive and contraceptive agreements and guidance provided in Section 10.4, Appendix 4.

Contraceptive use by men or women should be consistent with local regulations for those participating in clinical studies.

Informed Consent

12. Capable of giving signed informed consent as described in Appendix 1 which includes compliance with the requirements and restrictions listed in the informed consent form (ICF) and in this protocol

5.2. Exclusion Criteria

Participants are excluded from the study if any of the following criteria apply:

Medical Conditions

13. Class IV RA according to ACR revised response criteria
14. Have an abnormality in the 12-lead electrocardiogram (ECG) that, in the opinion of the investigator, increases the risks associated with participating in the study
15. Have presence of 1 or more significant concurrent medical conditions per investigator judgment, including but not limited to the following: poorly controlled diabetes or hypertension; chronic kidney disease stage IIIb, IV, or V; symptomatic heart failure (New York Heart Association class II, III, or IV); myocardial infarction or unstable angina pectoris within the past 12 months prior to randomization; severe chronic pulmonary disease (e.g., requiring oxygen therapy); and major chronic inflammatory disease or connective tissue disease other than RA
16. Have a history of chronic alcohol abuse, IV drug abuse or illicit drug abuse within 1 year before screening.
Note: Marijuana use is prohibited during participation in this study, regardless of local laws or if used for medical purposes. Cannabidiol (CBD) products may be used during the study if they are derived exclusively from hemp. Participants who use hemp-based CBD products must be on a stable dose for at least 10 days prior to randomization, and participants must remain on that stable dose during the study.
17. Have a Columbia-Suicide Severity Rating Scale (C-SSRS) ideation within 1 month prior to screening or any suicidal behavior within 3 months prior to screening and either ideation or suicidal behavior during screening prior to Visit 2
18. Have donated blood of more than a single unit of blood within 4 weeks before randomization (Visit 2) or intent to donate blood during the course of the study
19. Have a diagnosis or history of malignant disease within 5 years prior to baseline, with the exceptions of:
 - basal cell or squamous epithelial carcinomas of the skin that have been resected with no evidence of metastatic disease for 3 years, or
 - cervical carcinoma in situ, with no evidence of recurrence within the 5 years prior to baseline
20. Have presence of confirmed cervical dysplasia
21. Have had any surgical procedure (except for minor surgery requiring local or no anesthesia and without any complications or sequelae) within 12 weeks prior to screening, or any planned surgical procedure scheduled to occur during the study

22. Have received a Bacillus Calmette-Guerin (BCG) vaccination or BCG treatment within 12 months of screening; or received any other live vaccine(s) (i.e., live attenuated) within 3 months of screening, or intend to receive a live vaccine during the study
23. Have had any of the following types of infection within 3 months of screening or develops any of these infections before the randomization visit:
 - Serious (requiring hospitalization, and/or IV or equivalent oral antibiotic treatment)
 - Opportunistic (as defined in Winthrop et al. 2015)
 - Herpes zoster is considered active and ongoing until all vesicles are dry and crusted over
 - Chronic (duration of symptoms, signs, and/or treatment of 6 weeks or longer)
 - Recurring (including, but not limited to herpes simplex, herpes zoster, recurring cellulitis, chronic osteomyelitis)
 - Subjects with recurrent nonserious infections such as cellulitis and uncomplicated orolabial and/or genital herpes may be enrolled at the discretion of the investigator when deemed not to place subjects at an increased risk of complications
24. Have any of the following:
 - Human immunodeficiency virus (HIV) infection
 - Current infection with hepatitis B virus (HBV) (i.e., positive for hepatitis B surface antigen and/or polymerase chain reaction [PCR] positive for HBV DNA)
 - Current infection with hepatitis C virus (HCV) (i.e., positive for HCV RNA)
 - Active tuberculosis (TB)
25. Have or have had latent TB infection (LTBI) that has not been treated with a complete course of appropriate therapy as defined by the World Health Organization (WHO) and/or the United States Centers for Disease Control and Prevention (CDC), unless such treatment is underway, as per Section 8.2.6.
26. Current or recent acute active infection, or fever of 100.5°F (38°C) or above, at screening or baseline. For at least 30 days prior to screening, participants must have no symptoms and/or signs of confirmed or suspected infection, and must have completed any appropriate anti-infective treatment
27. Have estimated glomerular filtration rate from serum creatinine using the Modification of Diet in Renal Disease method of <60 mL/minute
28. Participants having contraindications to MRI (for example, claustrophobia, pacemakers, aneurysm clips, intraocular metallic fragments) or IV gadolinium diethylenetriamine penta-acetic acid ([Gd-DTPA]; moderate or severe renal insufficiency, prior allergic reaction to gadolinium-containing contrast media)
29. Are women who are currently pregnant or breastfeeding, or who intend to become pregnant or to breastfeed at any time during the study or within 20 weeks after receiving the last dose of study drug.

Prior/Concomitant Therapy

30. Currently receiving or have received any of the following therapies within 28 days prior to the screening MRI:

- MTX, hydroxychloroquine, sulfasalazine, or leflunomide at an unstable dose (defined as a change in prescription).
This also includes a planned dose change during the study (including initiation or discontinuation)
- Cyclophosphamide, azathioprine, cyclosporine, gold, mycophenolate mofetil, Prosofia column, or Tacrolimus
- Oral Janus kinase inhibitor (e.g., tofacitinib, baricitinib)
- Parenteral corticosteroids, including initiation of planned treatment during the study
Note: A single intra-articular corticosteroid injection is permitted within 28 days prior to the screening MRI if no more than 40 mg triamcinolone (or equivalent) is administered and no further injections are planned during the study. The treated joint should be excluded from any joint-specific evaluations during the study.
- A chronic narcotic drug at an unstable dose. This also includes planned increase/new prescription during the study

31. Have received any of the following biologic immunosuppressive therapies under the defined conditions or plan any such treatments during the study (other biologic agents may be allowed after discussion with the sponsor and upon agreement in writing):

- Etanercept, adalimumab, anakinra, infliximab, certolizumab pegol, golimumab, abatacept, or tocilizumab within 8 weeks prior to screening MRI
- B-cell-depleting agents (such as rituximab) or other cell-depleting biologics (e.g., anti-CD3 antibody) within 12 months prior to screening MRI

32. Have failed more than 2 bDMARDs or tsDMARDs (e.g. excluded if have failed 2 bDMARDs and 1 tsDMARD)

33. Have previously completed a clinical trial investigating any other molecule targeting PD-1 or have previously discontinued from this study after receiving LY3462817

Prior/Concurrent Clinical Study Experience

34. Are currently enrolled in any other clinical trial involving a study intervention or any other type of medical research judged not to be scientifically or medically compatible with this study

35. Have participated, within the last 30 days, in a clinical trial involving study intervention. If the previous study intervention has a long half-life, 3 months or 5 half-lives (whichever is longer) should have passed prior to screening

36. Have previously completed or withdrawn from this study

Other Exclusions

37. Are investigator site personnel directly affiliated with this study and/or their immediate families. Immediate family is defined as a spouse, parent, child, or sibling, whether biological or legally adopted.
38. Are Lilly employees or employees of third-party organizations involved with the study that require exclusion of their employees
39. Are not willing to receive IV injections
40. Are unsuitable for inclusion in the study, in the opinion of the investigator or sponsor, for any reason that may compromise the participant's safety or confound data interpretation

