7.1.2. Criteria for Permanent Discontinuation of Study Intervention

In rare instances, it may be necessary for a participant to permanently discontinue (definitive discontinuation) study intervention. If study intervention is definitively discontinued, the participant will be encouraged to remain in the study. See the SoA for data to be collected at the time of discontinuation of study intervention and follow-up and for any further evaluations that need to be completed.

Permanent discontinuation of study intervention should occur if the scenarios described occur during the study.

Participant decision

- The participant requests to discontinue the study intervention.

Investigator decision

- The investigator decides that the participant should be discontinued from the study intervention.

Pregnancy

- The participant becomes pregnant during the study (see Section 8.3.5 and Section 10.4, Appendix 4).

Safety considerations

The participant:

- Has a malignancy (except for successfully treated basal or squamous cell skin carcinoma)
- Answered "yes" to Question 4 or Question 5 on the "Suicidal Ideation" portion of the C-SSRS
- Answered "yes" to any of the suicide-related behaviors on the Suicidal Behavior portion of the C-SSRS
A psychiatrist or appropriately trained professional may assist in the decision to discontinue the participant.
- Is diagnosed with LTBI during the study and are not a candidate for treatment as described in Section 7.1.1.1, or
- Has a serious or opportunistic infection that in the opinion of the investigator merits the study intervention being discontinued. Such infections may include, but are not limited to:
 - HIV/acquired immune deficiency syndrome (AIDS) infection
 - active TB infection or untreated LTBI (see Sections 7.1.1 and 8.2.6)
 - HCV RNA positive (Section 8.2.8)
 - HBV DNA positive (Section 8.2.7).

The participant should be referred to, evaluated and managed by a specialist physician with expertise in evaluation and management of viral hepatitis prior to discontinuation of any

immunomodulatory and/or immunosuppressive therapy, including study intervention. Timing of discontinuation from study intervention relative to the initiation of any antiviral treatment for hepatitis is to be based on the recommendation of the consulting specialist physician, in conjunction with the investigator, and aligned with medical guidelines and standard of care.

Hepatic event or liver test abnormality

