8.2.5. Suicidal Ideation and Behavior Risk Monitoring

Participants being treated with the study intervention should be monitored appropriately and observed for suicidal ideation and behavior or any other unusual changes in behavior, especially at the beginning and end of the course of treatment, or at the time of dose changes, either increases or decreases. Consideration should be given to discontinuing the study medication in participants who experience signs of suicidal ideation or behavior, following a risk assessment.

Families and caregivers of participants being treated with the study intervention should be alerted about the need to monitor participants for the emergence of unusual changes in behavior, as well as the emergence of suicidal ideation and behavior and to report such symptoms immediately to the study investigator.

Baseline assessment of suicidal ideation and behavior and treatment emergent suicidal ideation and behavior will be monitored during Study KDAD using the C-SSRS.

C-SSRS Self-Harm Supplement and Follow-Up forms

The C-SSRS is a scale that captures the occurrence, severity, and frequency of suicidal ideation and behavior during the assessment period via a questionnaire. The scale was developed by the National Institute of Mental Health trial group (Treatment of Adolescent Suicide Attempters study) for the purpose of being counterpart to the Columbia Classification Algorithm of Suicide Assessment (C-CASA) categorization of suicidal events.

Consistent with Food and Drug Administration (FDA) regulatory guidance (FDA 2012), any occurrence of suicide-related thoughts and behaviors will be assessed as indicated in the SoA (Section [1.3](#)).

The Lilly Self-Harm Supplement should be completed every time the C-SSRS is administered. If, based on administration of the C-SSRS, it is determined that suicide-related behaviors have

occurred, then the Lilly Self-Harm Follow-Up form will be used to collect additional information to allow for a more complete assessment of these behaviors.

For this study, the C-SSRS is adapted for the assessment of the ideation and behavior categories only. The Intensity of Ideation and Lethality of Behavior sections are removed.

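### Exclusion criterion 17 uses *and* where *or* is probably meant: on either literal grouping, suicidal behavior before screening alone, or suicidality arising only in screening, does not exclude

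*Protocol*

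**What the plan says.** Any single exclusion criterion in Protocol Section 5.2 is enough to exclude. Criterion 17 is the only one that names suicidality. It has three limbs:

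- **A**: C-SSRS ideation within 1 month before screening.
- **B**: suicidal behavior within 3 months before screening.
- **C**: ideation or suicidal behavior during screening, before Visit 2.

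A is joined to B by *or*. B is joined to C by *and*: "any suicidal behavior within 3 months prior to screening and either ideation or suicidal behavior during screening prior to Visit 2". There is no comma, bullet or bracket.

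Other provisions bear on the same participants:

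- Criterion 15 excludes for "significant concurrent medical conditions per investigator judgment, including but not limited to the following", and its list of examples does not mention suicidality.
- Criterion 40 excludes people judged unsuitable "in the opinion of the investigator or sponsor, for any reason that may compromise" safety or data interpretation.
- Section 7.1.2 says "Permanent discontinuation of study intervention should occur if the scenarios described occur during the study". Its scenarios include a yes "to Question 4 or Question 5 on the" ideation part of the C-SSRS, and a yes to "any of the suicide-related behaviors on the Suicidal Behavior portion of the C-SSRS".
- Section 8.2.5, on participants under treatment, says "Consideration should be given to discontinuing the study medication in participants who experience signs of suicidal ideation or behavior, following a risk assessment".
- The Schedule of Activities (Section 1.3) places the screening C-SSRS at Visit 1 and the since-last-assessed version at Visit 2, before dosing.

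**The concern.** With *and* read as a conjunction, limb C narrows the exclusion when it should add to it. A recent suicide attempt before screening would then not exclude by itself, and neither would ideation or behavior that first appears between Visit 1 and Visit 2. That is an odd result for a criterion whose purpose is to keep people at current risk out of the study.

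What is at stake is participant safety and consistent eligibility across sites. Section 5 does not permit waivers, so the written criteria have to carry the rule. The wording also matters after enrollment. Section 7.2.1, and the United Kingdom rule in Appendix 10, require action when a participant did not meet the entry criteria. For someone with limb B only, whether that applies turns on how one conjunction is read.

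**Working it through.** There is no plan figure to reproduce. The check is a full enumeration of the cases.

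**Inputs.** A, B and C are the limbs of criterion 17. Because Section 7.1.2 acts on some C-SSRS answers and not others, split C into:

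- **C1**: screening-period ideation other than Question 4 or 5.
- **C2**: screening-period behavior, or Question 4 or 5 ideation.

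**Number of case types.** A is present or absent, B is present or absent, and C is none, C1 or C2. That gives 2 × 2 × 3 = 12, less the one with nothing present, so 11.

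**Possible groupings of the written text.** G1 is (A or B) and C. G2 is A or (B and C). The comparison form is A or B or C.

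| Case type | G1 | G2 | A or B or C |
|---|---|---|---|
| B only | not excluded | not excluded | excluded |
| C1 only | not excluded | not excluded | excluded |
| C2 only | not excluded | not excluded | excluded |
| A only | not excluded | excluded | excluded |
| A and B, no C | not excluded | excluded | excluded |
| A with C1; A with C2 | excluded | excluded | excluded |
| B with C1; B with C2 | excluded | excluded | excluded |
| A and B with C1; A and B with C2 | excluded | excluded | excluded |

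**Counts.**

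- G1 excludes 3 × 2 = 6 and leaves 11 − 6 = 5.
- G2 excludes 2 × 3 + 2 = 8 and leaves 11 − 8 = 3.
- Excluded on both: 6. Dependent on the grouping: 8 − 6 = 2. Excluded on neither: 11 − 8 = 3. Total: 6 + 2 + 3 = 11.
- *Or* throughout excludes all 11.

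Without the split of C there are 7 non-empty combinations. G1 excludes 3, G2 excludes 5 and *or* throughout excludes 7. B alone and C alone still fail both groupings.

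**Credit for Section 7.1.2.** In the C2-only case, the Visit 2 C-SSRS before dosing would give an answer that Section 7.1.2 lists as a reason to stop study drug. That points against dosing, although it does not make the person ineligible. Removing that case leaves 5 − 1 = 4 case types under G1 and 3 − 1 = 2 under G2 with no explicit rule free of judgment. The 2 are B only and C1 only. The 4 add A only, and A and B without C.

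**How the protocol uses the two words elsewhere.** Criterion 23 joins the same pair of time windows with *or*: "within 3 months of screening or develops any of these infections before the randomization visit". Criterion 26 uses *or* between screening and baseline. Inclusion criterion 3 requires joint counts at screening *and* baseline, where both are plainly needed. A site that follows the protocol's own usage could fairly read the *and* in criterion 17 as requiring both.

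**The case against.** The strongest reply is that ordinary English allows an additive *and*: the listed histories exclude, and so does suicidality in screening. That reading leaves no gap and fits the rest of the protocol better, since it would be strange to admit someone whose screening-period behavior Section 7.1.2 treats as a reason to stop drug. This stands as an account of what was probably meant. It does not settle what the sentence says, and criterion 23 shows the clearer wording was available.

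Second, there are safeguards. Criteria 15 and 40 allow exclusion, criterion 40 gives that power to the sponsor as well as the site, and the introduction to Section 8 asks that immediate safety concerns be discussed with the sponsor. These lower the practical risk, but each rests on judgment.

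Third, the Section 7.1.2 items turn on having answered yes, and a C-SSRS is completed at Visit 1, so that section might be read to reach behavior before screening. It governs scenarios that arise during the study, however. Stretching it back would make the 3-month window in criterion 17 redundant and could catch lifetime history.

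Fourth, the counts are logical cells, not frequencies, and the total of 11 depends on splitting C but not A. That is correct, and they should be read only as a map of the gap. It is also fair that suicidality is not among the adverse events of special interest in Section 8.3.6, and that no misreading by a site is shown.

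**Conclusion.** The concern holds as a wording defect in an operative safety criterion. On either literal grouping, suicidal behavior in the 3 months before screening alone, or suicidality arising only during screening, does not meet criterion 17. New behavior or Question 4 or 5 ideation in screening is partly covered, because Section 7.1.2 points against dosing. Behavior before screening alone, and lower-level ideation first seen in screening, are left to judgment. On the narrower grouping, (A or B) and C, ideation before screening without a screening-period finding is left to judgment as well.

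This rests on reading *and* as a conjunction and on Section 7.1.2 applying to events during the study. Under the additive reading there is no gap. The number of participants affected cannot be estimated from the documents. The point should be corrected, but it does not bear on the statistical conclusions.

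**What to change.** In criterion 17, replace *and either* with *or either* and letter the limbs as alternatives:

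- (a) C-SSRS ideation within 1 month before screening; OR
- (b) any suicidal behavior within 3 months before screening; OR
- (c) ideation or suicidal behavior during screening, before Visit 2.

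Change nothing else in the criterion. The sponsor should confirm that three separate triggers are intended; if a conjunction was meant, this edit would change eligibility.

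The cost is one word plus lettering in the next amendment, with the ethics review that any amendment needs (Appendix 1, Section 10.1.1). No new assessment is required, because the C-SSRS is already scheduled at Visits 1 and 2. There may be a few more screen failures. They would be final, because criterion 17 is not among those for which Section 5.4 allows rescreening.
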